(3) adequate introduction to the computer program by staff to reduce possible anxiety about use of the system, (4) provision of follow-up consultation with a clinician if needed, and (5) supervision of the treatment process by a clinician^{[256](#), [257](#)}.

Computer-based interventions have been used safely in multiple investigations with a range of populations^{[117](#), [258-260](#)}, and we are unaware of any reported risks associated with these interventions. A recent Agency for Healthcare Research and Quality (AHRQ) comprehensive review of computer-assisted interventions for a wide range of health and mental health issues found no reports of adverse events associated with these programs^{[110](#)}. Similarly, the CBT4CBT program was not associated with any adverse events in our previous trials with a comparatively severe drug using population nor in our *completed* R21 pilot study with an alcohol using sample^{[119](#), [122](#), [123](#)}.

Thus, while we believe adverse events are likely to be rare, because the proposed trial includes an evaluation of the CBT4CBT version delivered as an approximation of a ‘stand-alone’ intervention, special efforts will be made to monitor patient safety and response closely. In addition to weekly assessments that include breath and urine monitoring taken on the schedule of the clinic and self-reports of substance use, the ‘CBT4CBT’ virtual standalone condition will be implemented with one 10-minute or less, manual-guided, clinician monitoring session per week delivered by a trained and supervised master’s level MCCA or SATU clinician supervisor. This will enable us to monitor each participant’s clinical status closely and thus address potential Human Subjects concerns associated with evaluation of a ‘stand-alone’ computer-based intervention for treatment seekers. *Participants assigned to this condition who show significant psychological or symptomatic deterioration will be withdrawn from this condition and referred immediately to the appropriate level of treatment (consistent with criteria for withdrawal from the other treatment conditions).*

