- Provision of monitoring and limited clinician support. Participants assigned to the CBT4CBT condition will also meet weekly with a trained MCCA or SATU clinician for a 'monitoring/support' visit per clinic policy. These brief (10 minutes maximum) monitoring/support manual-guided visits will take place at the time of the weekly

assessment sessions and follow guidelines for low-intensity interventions used in previous placebo-controlled trials^{159,210} and are intended to provide a means of closely monitoring each participants' status, inquire as to whether the participant has any questions or concerns, and assess availability and use of supports. We have modified our 'Clinical Management' manual¹⁶³, modeled on that used in Project Combine¹⁶⁰, and which has been used as a low-intensity monitoring/support condition in multiple previous trials, for this use. These sessions will be taped and monitored for fidelity.

- Participants in all conditions are also able to call the MCCA or SATU on-call clinician at any time should questions or concerns arise; emergency services are available through MCCA or SATU.

We have used similar procedures to monitor participant response and safety in several previous studies evaluating a range of types and intensities of behavioral therapies, as well as in our recently completed R21 pilot trial evaluating CBT4CBT for alcohol use disorders. As in the proposed study, participants in the R21 pilot trial (and all conditions) were monitored weekly by research staff; participants whose frequency or intensity of alcohol or drug use worsened or did not improve were evaluated by the Project Director for possible withdrawal from the treatment arm of the study with referral to inpatient or intensive day treatment (i.e., higher level of care). Of 24 participants assigned to the CBT4CBT condition with brief clinical monitoring in that study, only one was withdrawn from the treatment arm of the study and referred to intensive day treatment. No other adverse or serious adverse events were seen in that condition.

10. Data and Safety Monitoring Plan: Include an appropriate Data and Safety Monitoring Plan (DSMP) based on the investigator's risk assessment stated below. (Note: the HIC will make the final determination of the risk to subjects.) For more information, see the Instructions, page 24.

- a. What is the investigator's assessment of the overall risk level for subjects participating in this study? Minimal Risk

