- b. If children are involved, what is the investigator's assessment of the overall risk level for the children participating in this study?
- c. Copy, paste, and then tailor an appropriate Data and Safety Monitoring Plan from <http://www.yale.edu/hrpp/forms-templates/biomedical.html> for
 - i. Minimal risk
 - ii. Greater than minimal/moderate risk
 - iii. High risk

A Data and Safety Monitoring Board (DSMB) will monitor this project. This board, is already in place for the Yale Psychotherapy Development Center, monitors all of [name] clinical trials. The DSMB is composed of Yale investigators (Drs. [name], [name], [name]) who are independent of the proposed trial and experienced in various aspects of the conduct of clinical trials for the treatment of addictive disorders. We have developed a standard DSMB report form that is used in all Center and Center-related trials that summarizes, *on a quarterly basis*:

1. Recruitment, retention, and follow-up rates for the study and compares them to target rates.
2. Rates of data completeness and availability of primary outcome data

3. Occurrence of AEs and SAEs
4. Report of study progress since the last report.
5. Rates of recruitment of women, minorities, and children with respect to targets.

These reports are generated by the Data Manager each quarter, reviewed and signed by [name] prior to their submission to the DSMB. DSMB comments are documented and forwarded to the Yale IRB at the time of the annual review and re-approval.

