Because the projected effect sizes may not be large enough for detection during interim analyses, we are not proposing a preliminary analysis of accumulating efficacy and feasibility data by treatment assignment. Instead, we propose to submit a quarterly report of aggregate data to the DSMB members that contains screening data, baseline demographics, retention data, serious adverse events data, as well as accrual status including projections, times to milestones, and any other data that will help in the assessment of the clinical trial. Based on this report, each DSMB member will complete a form making one of two recommendations: 1) continue recruitment as planned; or 2) schedule formal DSMB meeting immediately. If any DSMB member recommends a meeting, this will be scheduled within one week, minutes will be kept, the report will be reviewed with [name], and the committee will vote on whether the study should: 1) continue recruitment unchanged; 2) continue with a protocol amendment; 3) stop recruiting pending further investigation. If, after this meeting, any DSMB member votes to stop recruitment or requests a protocol modification, the Yale IRB will be informed.

Participants who experience a significant psychiatric or medical problem requiring an overnight hospitalization at an acute care facility will be considered to have experienced an SAE. In general, most SAEs will result in inpatient care and thus in transfer from MCCA or SATU. All SAEs will result in the completion of an SAE Form and a verbal report within one hour to the Principal Investigator ([name]) and the MCCA Clinic Director, [name], or the SATU Clinical Director, [name]. Within 24 hours, the following additional individuals will be informed: 1) all co-investigators; 2) the DSMB. All of these individuals will receive a copy of the SAE Form within one week at which point a decision will be made whether to convene a meeting of the DSMB. Adverse events that are serious and unanticipated and probably, possibly, or definitely related or adverse events occurring with greater frequency than anticipated will be reported to Yale Human Investigation Committee within 48 hours of discovery.

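### The quarterly DSMB report is pooled over arms, so the plan gives the board no by-arm summary of SAEs, AEs, deterioration withdrawals or retention, although stand-alone CBT4CBT is singled out for special safety monitoring

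*Combined protocol and SAP*

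**What the plan says.** **Reporting to the DSMB (Section V, item 10).** On by-arm interim work the plan says: "we are not proposing a preliminary analysis of accumulating efficacy and feasibility data by treatment assignment". The reason given is that the projected effects may be too small to detect at an interim look. In place of that analysis, "we propose to submit a quarterly report of aggregate data to the DSMB members". The report covers screening, baseline, retention, SAE and accrual data, and closes with an open item: "any other data that will help in the assessment of the clinical trial". The standard report form also lists "Occurrence of AEs and SAEs". On the basis of the report, each member recommends either continuing recruitment or holding an immediate formal meeting. A named person reviews and signs the report before it goes to the board.

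**Individual SAEs (same item).** An SAE is a psychiatric or medical problem that leads to an overnight stay in an acute care facility. For each one: "Within 24 hours, the following additional individuals will be informed: 1) all co-investigators; 2) the DSMB". Then: "All of these individuals will receive a copy of the SAE Form within one week". A decision on convening the board follows.

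**The arm of interest.** Item 8 (Risks) notes that CBT4CBT is tested here as something close to a stand-alone treatment, and for that reason "special efforts will be made to monitor patient safety and response closely". Item 9 (Minimizing Risks) gives the level of clinician interaction as the chief difference from the other conditions. It also reports the pilot: of 24 participants given CBT4CBT with brief monitoring, "only one was withdrawn from the treatment arm of the study and referred to intensive day treatment".

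**The concern.** The reason for not splitting data by arm is about power for efficacy. It does not explain why safety data should be pooled over three conditions with very different clinician contact.

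The arm-specific safety question is the protocol's own: does minimal clinician contact let more people deteriorate? The safeguards in items 8 and 9 act on the individual participant. None of them tells the board whether deterioration is more frequent in one arm. If it were, members could vote to continue each quarter on a pooled figure that gives no hint of where the events lie.

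**Working it through.** The documents give no boundary, threshold or detection probability for safety, so there is no planned figure to reproduce. The check has two parts.

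**1. What reaches the board, by type of event**

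| Event | Individual report to DSMB | Named in quarterly report | By-arm display described |
|---|---|---|---|
| SAE | Yes: notice in 24 hours, form in one week; arm on the form not stated | Yes | No |
| AE that is not an SAE | None described | Yes | No |
| Withdrawal for deterioration, no overnight stay | None described | No; at most within AE or retention figures | No |
| Retention | Not applicable | Yes | No |

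The pilot event shows why the third row matters. That participant was referred to intensive day treatment. On the facts given, this is not an overnight acute-care stay, so under this protocol's definition it would not be an SAE and would not produce an SAE form.

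Pooled retention is also hard to read. Pilot completion (C.1.e) was 23% in TAU, 59% in TAU plus CBT4CBT and 63% in CBT4CBT only. With gaps of that size, one overall figure says little about any single arm.

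**2. What pooling hides**

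Inputs: 60 per arm and 180 in all (Adequacy of sample size); pilot rate 1/24 = 4.2%, exact 95% CI 0.1% to 21.1%. All other rates below are assumptions.

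*Simple illustration.* Assume 10% in CBT4CBT and 2% in each other arm:

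(0.10 × 60 + 0.02 × 120)/180 = (6 + 2.4)/180 = 4.7%

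If the other arms instead ran at the pilot's 4.2%:

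(6 + 5)/180 = 6.1%

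*Same total, different splits.* Each row pools to 15/180 = 8.3%. The p-values are two-sided Fisher exact.

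| CBT4CBT | Other two arms | p |
|---|---|---|
| 5/60 (8.3%) | 10/120 (8.3%) | 1.00 |
| 10/60 (16.7%) | 5/120 (4.2%) | 0.008 |
| 12/60 (20.0%) | 3/120 (2.5%) | 0.0002 |

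*Chance of a flag at full enrolment.* Take 1/24 as a known background rate and flag at one-sided exact binomial 0.05. The pooled rule is at least 13/180 (false-flag probability 0.039). The arm rule is at least 6/60 (0.038). The last column drops the known background and compares CBT4CBT with the other two arms by one-sided Fisher test at 0.05.

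| CBT4CBT rate | Pooled flag | Arm flag | CBT4CBT vs others |
|---|---|---|---|
| 8.3% (2×) | 0.20 | 0.38 | 0.21 |
| 12.5% (3×) | 0.48 | 0.78 | 0.52 |
| 16.7% (4×) | 0.75 | 0.95 | 0.79 |

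The pooled and arm flags both need a trusted background rate, and one event in 24 does not supply one. Without it, a pooled count has nothing to be judged against, while arm-level counts can still be compared with each other.

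**The case against.** A reader might infer that the board receives only aggregate data and cannot see an excess of SAEs in one arm. The documents do not support that. The board hears of every SAE within a day and gets the form within a week, and the form may show the arm. The sentence that declines by-arm analysis names efficacy and feasibility, not safety, so a by-arm safety display is left undescribed rather than forbidden. The report may include other helpful data, and any one member can force a meeting within a week.

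Nor do the documents show that deterioration withdrawals never reach the board. AEs and retention are on the quarterly form. After describing the pilot withdrawal, item 9 says that no other adverse events were seen in that condition, which suggests that such a withdrawal may be counted as an AE.

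Other safeguards exist. All arms are assessed weekly, an independent evaluator decides on withdrawal, and AEs more frequent than anticipated go to the ethics committee within 48 hours.

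All of this stands against the stronger reading. It does not close the gap. Freedom to add data is not a plan to add it, single forms give no rates, and a trigger based on frequency needs a frequency by arm if the worry is one arm.

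The illustration also has limits that must be conceded. The 10% and 2% are assumed. It is tempting to say that 4.7% would pass for the pilot's 4.2% and so hide a five-fold excess, but an interval of 0.1% to 21.1% defines no expected rate and includes 10% itself. By-arm counts would often be inconclusive too: 6/60 against 3/120 gives p = 0.06, and at half enrolment 3/30 against 1/60 gives p = 0.11. Pooled monitoring is weaker, not blind.

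**Conclusion.** The concern holds in a limited form. The report on which the board votes is aggregate, and no by-arm summary of SAEs, AEs, deterioration withdrawals or retention is provided for. The stated reason for avoiding by-arm analysis does not extend to safety, and the protocol itself marks one arm for special monitoring. The gap is widest for deterioration without an overnight stay, which has no individual reporting route to the board and no named line in its report.

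The structural point, that one pooled total fits very different splits, needs no assumption. The size does. At three times the pilot rate in CBT4CBT, a pooled flag fires with probability 0.48 and an arm-level flag with 0.78, given a background of 1/24 that rests on one event. This is a cheap improvement for patient safety. It is not evidence that any arm is unsafe, or that the board would miss individual SAEs.

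**What to change.** - Add a closed section to the quarterly DSMB report with arms coded A, B and C, which the board can unmask on request. Give counts and denominators for SAEs, AEs, deterioration withdrawals and retention.
- Name deterioration withdrawals as a report item, and say whether they are also recorded as AEs.
- Have the data manager send the closed section directly to the DSMB, outside the current review-and-sign step.
- State the coded arm on SAE forms sent to the DSMB.
- Describe the tables as descriptive safety monitoring, with no formal efficacy test and no efficacy stopping rule.

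The cost is one extra set of tables each quarter and some handling of arm-level data by the data manager. There is one real drawback. Deterioration includes marked increases in drinking, so these counts partly overlap the drinking outcome and cannot be wholly free of efficacy information. By-arm retention may likewise be part of the feasibility data that the plan chose not to split. The plan should acknowledge both and restrict the closed section to the board.

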- Data from our recently completed R21 evaluating the alcohol version of CBT4CBT (including CBT4CBT delivered with brief clinical monitoring) indicates that this approach is feasible, safe and well-accepted by individuals with alcohol use disorders. *Preliminary data further indicate CBT4CBT is effective at increasing the percentage of days abstinent and the percentage of subjects with no heavy drinking days compared to standard treatment only.*
- Our published and preliminary data highlight the relevant experience and developing expertise of New Investigator [name] (PI), with respect to evaluation of mechanisms of behavior change in computerized CBT^{96, 122, 131, 153, 159, 163}.

C.2. RESEARCH PLAN

C.2.a. Overview

One hundred eighty individuals seeking treatment for alcohol use at the MCCA program in Bridgeport or New Haven, CT or SATU in New Haven will be randomized to (1) standard treatment as usual (TAU) at MCCA or SATU, (2) clinician-delivered CBT, or (3) CBT4CBT for alcohol use disorders (with brief clinical monitoring). Treatments will be delivered over an 8-week period with a six-month follow-up after termination of the study treatments, consistent with prior trials of CBT4CBT^{119, 122}. The primary outcome measure will be the percentage of days abstinent from alcohol (measured via Timeline FollowBack⁴), with secondary measures to include percentage of heavy drinking days, percentage of positive urine ethyl glucuronide (EtG), drinking-related consequences, quality of life, and cost effectiveness.

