Latent growth curve modeling will be the principal strategy for evaluating mediation using Mplus version 7²⁵¹. The product of coefficients method^{18, 19} will be

used to determine the mediating effects of skills acquisition during the treatment period *on PDA* during follow-up. In this model (Figure 4), M_1 through M_3 are repeated measures (weeks 0, 4, 8) of the mediator ‘acquisition of skills’ (as measured by ARRT¹⁵, CSI¹⁶, homework completion and quality, and knowledge assessment⁵⁰). Both the intercept (I_M) and slope (S_M) act as joint mediators of the effect of X (treatment condition) on Y (PDA during 6 month follow-up), allowing the examination of the average level (i.e., intercept) and average change over time (i.e., slope) of the mediator. We will be using the 6-month period following treatment as our alcohol use outcome in this model to support the temporal relation criterion⁶⁴, as well as to evaluate the delayed emergence of CBT’s effect on alcohol use¹³⁹. This model will test:

- **H2a:** Effect of CBT on acquisition of skills (a_2 path: $X \rightarrow M$): Clinician-CBT>TAU; CBT4CBT>TAU
- **H2b:** Effect of change in acquisition of skills on PDA by month during follow-up (b_2 path: $M \rightarrow Y$)
- **H2c:** Indirect effect of CBT on PDA via change in acquisition of skills ($a_2 * b_2 / se_{a2} * se_{b2}$)

Adequacy of sample size: Parameter estimates from our initial trial of CBT4CBT that supported coping skills acquisition as a mediator of treatment effects on substance use⁹⁶ were used to estimate effect sizes of treatment condition on PDA via skills acquisition ($a=.26$; $b=.59$). Based on these effect sizes and power estimates for testing mediation derived from a simulation study⁹⁴, we will have adequate power (.80) to detect significant mediating effects with the proposed sample size of 60 per condition.

Exploratory Aims:

[figure not shown]

(a) Pre-treatment cognitive function as indicated by measures from CANTAB tasks (sustained attention,

working memory, response inhibition, cognitive flexibility, planning, decision-making) will be evaluated as moderators of CBT's effect on PDA (clinician-delivered CBT and CBT4CBT vs. TAU), using linear moderation regression models, such that a significant interaction between pre-treatment cognitive function measures and treatment condition would indicate a moderated effect (i.e., the effect of CBT on PDA is dependent on levels of pre-treatment cognitive function);

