The procedures for SAE reporting include written documentation using the clinical notes related to the adverse event and specific forms detailing the event with a sign-off by all appropriate supervisory personnel. Communication of recommendations and decisions from all parties (DSMB, Yale Human Investigations Committee, and MCCA or SATU Administration) are made back to the investigator in a timely manner. We will report all protocol amendments or changes in the informed consent form to NIAAA as well as any temporary or permanent suspension of patient accrual.

- d. For multi-site studies for which the Yale PI serves as the lead investigator: **N/A**
 - i. How will adverse events and unanticipated problems involving risks to subjects or others be reported, reviewed and managed?
 - ii. What provisions are in place for management of interim results?

iii. What will the multi-site process be for protocol modifications?

11. Statistical Considerations: Describe the statistical analyses that support the study design.

Aim 1 - Evaluation of treatment effects:

The principal strategy for assessing the efficacy of the study treatments on outcome will be random effects regression models for continuously measured primary (e.g., percentage of days abstinent - PDA) and secondary (e.g., percentage of heavy drinking days, quality of life, etc.) outcomes. Our research group has used these methods to evaluate main and interaction effects, with appropriate covariates (e.g., retention, compliance with treatment) in multiple previous trials^{121, 138, 142, 171, 172}. We will include treatment utilization data during the follow-up period as a covariate in analyses evaluating treatment effects through follow-up.

Analysis of treatment effects at post-treatment and follow-up will include the following contrasts:

- **H1a:** *Main effect for CBT on PDA by month during treatment:* Clinician-CBT and CBT4CBT>TAU.
- **H1b:** *Main effect for CBT on PDA by month through follow-up:* Clinician-CBT and CBT4CBT>TAU.

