Adequacy of sample size: *H1a* – Using conventional effect size estimates, we determined that our proposed sample size of 60 per condition would be sufficient for detecting a small-medium effect ($d=.35$) of treatment on PDA using a random effects regression model (2 groups, PDA by month, 3 data points, ICC=.6, alpha=.05, beta=.80). *H1b* – The proposed sample is sufficient to detect a medium effect ($d=.50$) through the follow-up period with a random effect regression model (2 groups, PDA by month, 7 data points, ICC=.6, alpha=.05, beta=.80). These effect sizes are conservative, based on estimates from completed studies of CBT4CBT^{119, 122}.

Power calculations	Power	Estimated effect size	# of datapoints	Sample size per cell
H1a: (Clinician CBT + CBT4CBT stand-alone) v TAU, main effect for active treatment	.80	.35	3	60
H1b : (Clinician CBT + CBT4CBT stand-alone) v TAU, main effect for follow up	.80	.50	7	60

Aim 2 – Evaluation of skills acquisition as mediator of CBT effects:

Latent growth curve modeling will be the principal strategy for evaluating mediation using Mplus version 7²⁵¹. The product of coefficients method^{18, 19} will be used to determine the mediating effects of skills acquisition during the treatment period on PDA during follow-up. We will be using the 6-month period following treatment as our alcohol use outcome in this model to support the temporal relation criterion⁶⁴, as well as to evaluate the delayed emergence of CBT's effect on alcohol use¹³⁹. This model will test:

- **H2a:** *Effect of CBT on acquisition of skills (a₂ path: X→M):* Clinician-CBT>TAU; CBT4CBT>TAU
- **H2b:** *Effect of change in acquisition of skills on PDA by month during follow-up (b₂ path: M→Y)*

- **H2c:** *Indirect effect of CBT on PDA via change in acquisition of skills ($a_2 * b_2 / se_{a2} * se_{b2}$)*

Adequacy of sample size: Parameter estimates from our initial trial of CBT4CBT that supported coping skills acquisition as a mediator of treatment effects on substance use⁹⁶ were used to estimate effect sizes of treatment condition on PDA via skills acquisition ($a=.26$; $b=.59$). Based on these effect sizes and power estimates for testing mediation derived from a simulation study⁹⁴, we will have adequate power (.80) to detect significant mediating effects with the proposed sample size of 60 per condition.

SECTION VI: RESEARCH INVOLVING DRUGS, BIOLOGICS, RADIOTRACERS, PLACEBOS AND DEVICES

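### The power of .80 printed for both H1a and H1b cannot be right for both: on the same inputs, one row at .80 puts the other near 98–99% or 46–50%

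*Combined protocol and SAP*

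**What the plan says.** The sample-size paragraph for Aim 1 appears twice, in Section V, C.2.f and in Section V, item 11 (Statistical Considerations). For H1a it says that "our proposed sample size of 60 per condition would be sufficient for detecting a small-medium effect ($d=.35$) of treatment on PDA". The inputs listed for that row are 2 groups, 3 monthly points, ICC .6 and alpha .05, in a random effects regression. For H1b it says that "The proposed sample is sufficient to detect a medium effect ($d=.50$) through the follow-up period", and the inputs listed are "PDA by month, 7 data points, ICC=.6, alpha=.05, beta=.80".

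The table in item 11 prints power .80 and 60 per cell in both rows, with effect sizes .35 and .50. The contrasts are the same: "Clinician CBT + CBT4CBT stand-alone) v TAU, main effect for active treatment" for H1a and "Clinician CBT + CBT4CBT stand-alone) v TAU, main effect for follow up" for H1b. The table shows that the text's beta of .80 is meant as power.

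The plan does not say whether the test is one- or two-sided, which months make up the 3 and 7 points, whether baseline PDA is a data point or a covariate, or what attrition is allowed for.

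**The concern.** Only two inputs differ between the rows, the effect size (.35 v .50) and the number of points (3 v 7). With a single ICC of .6, both differences raise the power of H1b. Two equal power figures therefore conflict with each other before any absolute power is computed.

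PDA is the primary outcome and H1a is its during-treatment contrast. If the H1b row is the correct one, H1a has about an even chance of detecting d = .35. If the H1a row is correct, H1b is harmlessly understated. The text does not let a reader tell which case applies.

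**Working it through.** **Inputs.** From item 11: d = .35 with k = 3 points (H1a), d = .50 with k = 7 points (H1b), r = ICC = .6, alpha = .05, 60 per arm. The pooled contrast is 120 v 60; a single CBT arm against TAU is 60 v 60. Sidedness is not stated, so both are shown (z = 1.960 or 1.645).

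**Formula.** SE² = (1/n₁ + 1/n₂) × F, and power = Φ(d/SE − z). For a time-averaged main effect under exchangeable correlation, F = (1 + (k − 1)r)/k:
- k = 3: (1 + 2 × .6)/3 = .733
- k = 7: (1 + 6 × .6)/7 = .657

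**Attempt to reproduce the plan's .80 and .80.** Pooled, two-sided, full retention, with 1/120 + 1/60 = .025:
- H1a: SE = √(.025 × .733) = .135; .35/.135 = 2.585; Φ(2.585 − 1.960) = 73.4%
- H1b: SE = √(.025 × .657) = .128; .50/.128 = 3.901; Φ(3.901 − 1.960) = 97.4%

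Neither is .80. A noncentral t calculation gives 72.9% and 97.3%.

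**Consistency check that does not depend on n.** Sample size and allocation cancel in the ratio of the two d/SE values:

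R = (.50/.35) × √(.733/.657) = 1.509

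- If H1a = .80, H1b = Φ((z + .842) × R − z) = 98.8% two-sided, 98.2% one-sided.
- If H1b = .80, H1a = Φ((z + .842)/R − z) = 45.9% two-sided, 50.1% one-sided.
- Ignoring the extra data points (R = 1.429), the two-sided values are 97.9% and 50.0%.

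For both rows to equal .80, F at 7 points would have to be (.50/.35)² = 2.04 times F at 3 points. It is .657/.733 = .896 times.

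**Other models with the stated ICC (exchangeable).** Power is two-sided, pooled, at full retention.

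| Model | F, k = 3 | F, k = 7 | Ratio | H1a | H1b |
|---|---|---|---|---|---|
| Time-averaged, all points | .733 | .657 | .896 | 73.4% | 97.4% |
| Mean of post-baseline months only | .800 | .667 | .833 | 70% | 97% |
| Change from baseline | .600 | .467 | .778 | 81.5% | 99.6% |
| Baseline as covariate (ANCOVA) | .440 | .307 | .697 | 92% | >99% |
| Group-by-linear-time | .800 | .514 | .643 | 70% | 99% |

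Other same-model pairs (H1a/H1b) are 82.6/98.8% for pooled one-sided time-averaged, 61.0/92.2% for 60 v 60 two-sided time-averaged, and 48.3/78.2% for a single time point at 60 v 60. No row or pair gives .80 twice.

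**Retention.** To reconcile the rows, H1b's effective sample would have to be 1/R² = 44% of H1a's. The protocol cites more than 80% retained at 6 months in its two earlier trials (C.1.a) and follow-up approaching 90–95% (C.2.c, item 4). With H1b at 80% and H1a complete, H1a = .80 still implies H1b of about 97%.

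Absolute two-sided power at 100/90/80% retained, treating loss as a reduction in complete cases:
- H1a time-averaged: pooled 73/69/64%; 60 v 60 61/57/52%
- H1a ANCOVA: pooled 92/89/85%; 60 v 60 82/78/73%
- H1b time-averaged: pooled 97/96/94%; 60 v 60 92/89/86%

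**The case against.** The strongest reply is that .80 is a threshold met by each row, not a computed value: the paragraph says the sample is sufficient for effects it calls conservative. H1b then passes easily. H1a also passes if baseline is one of the 3 points (81.5% as a change score, 92% by ANCOVA, pooled). The counts fit that reading. C.2.a states "Treatments will be delivered over an 8-week period with a six-month follow-up after termination of the study treatments", that is two treatment months and six follow-up months, so one anchor point plus 2 or 6 gives 3 or 7. The Aim 2 model likewise uses a series that includes week 0 ("are repeated measures (weeks 0, 4, 8) of the mediator").

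This has force, and H1a may well be adequately powered. But nothing says that baseline PDA is a point or covariate in Aim 1, and H1a itself is described only as "Main effect for CBT on PDA by month during treatment". The table prints .80 in a column headed Power, and for H1b that number is wrong as a power figure under the reading offered.

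A second reply is that the correlation may not be exchangeable. Replacing the ICC by AR(1) decay with r = .6 gives F ratios of .62 (average), 1.18 (change) and 1.57 (slope). The last two narrow the gap: H1a = .80 then implies H1b of about 96% or 89%. With an AR(1) slope test and 80% retention in H1b only, that falls to 81.5%. However, absolute H1a power for the pooled slope test is then only about 50%. The AR(1) change-score pair is 67.6/88.8% pooled and 55.2/78.5% at 60 v 60.

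A baseline-adjusted model with random-slope variance .077 per month² gives 80.7% in both rows. It needs a month-6 variance of about 1 + 36 × .077 = 3.8 times baseline, against a plan that states one ICC and a main effect. So the exact 98–99% and 46–50% depend on the model, but the reconciling cases leave the stated inputs.

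The follow-up analysis also adds treatment utilization as a covariate. Neither power statement makes any allowance for it.

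**Conclusion.** The concern holds. On the stated inputs (one ICC read as exchangeable, a main effect, the same n, alpha and contrast), the two .80 figures are mutually inconsistent whatever the sidedness, pooling or sample size. For the time-averaged test, one row at .80 puts H1b at about 98–99% or H1a at about 46–50%.

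The consequence is moderate. H1b's .80 is an understatement, so the claim of a sufficient sample stands for follow-up, though the figure is a wrong benchmark for durability. H1a's power at d = .35 could be about 70%, 73%, 82% or 92% pooled, depending on which months enter, sidedness and how baseline is used, and the plan does not settle these. The retention figures assume that lost participants contribute nothing; a random effects model using partial data would lose less.

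**What to change.** Recompute both rows under one declared model and restate them in C.2.f and in item 11 with its table. State:
- whether the test is one- or two-sided;
- the 120 v 60 allocation of the pooled contrast, with CBT4CBT v TAU at 60 v 60 shown beside it;
- which months form the 3 and the 7 points;
- whether baseline PDA is a data point or a covariate;
- the expected retention.

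Two examples at two-sided .05:
- *Time-averaged, no baseline adjustment, full retention:* H1a (d = .35) 73% pooled and 61% for CBT4CBT v TAU; H1b (d = .50) 97% and 92%. At 80% retained: 64% and 52%; 94% and 86%.
- *Baseline PDA as covariate, assuming ICC .6 also holds between baseline and later months, full retention:* H1a 92% and 82%; H1b above 99% for both. At 80% retained: 85% and 73%; above 99% for both.

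Correct beta to power in the text at the same time. The cost is a text and table edit, with no change in sample size, endpoint or contrast. The one drawback is that the H1a figure may become less favourable, depending on the model declared.
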